7.4.2.2 Cumulative incidence by visit

The cumulative incidence of newly diagnosed HCC and the cumulative incidence of disease progression at week 48, week 96, week 144, and week 192 will be estimated from the Kaplan–Meier analysis. Event or censoring rules are the same with cumulative incidence of week 240, as described in section 7.4.1. Figures of nominal cumulative incidence of HCC/disease progress by each visit will be product respectively.

7.4.2.3 Other secondary variables

The number and percentage will be presented respectively for secondary variables including:

- The proportion of subjects with serum HBV DNA < 20 IU/mL or serum HBV DNA < 69 IU/mL (Roche COBAS Taqman HBV Test) at Week 12, Week 24, Week 36, Week 48, Week 96, Week 144, Week 192 and Week 240.
- The proportion of subjects with serum HBV DNA < 20 IU/mL (Roche COBAS Taqman HBV Test) by baseline HBeAg status (HBeAg Positive and HBeAg Negative) at Week 48, Week 96, Week 144, Week 192 and Week 240.
- The proportion of subjects with serum HBV DNA < 20 IU/mL (Roche COBAS Taqman HBV Test) by baseline HBV DNA level ($\geq 6 \text{ Log}_{10} \text{ IU/mL}$ and $< 6 \text{ Log}_{10} \text{ IU/mL}$) at Week 48, Week 96, Week 144, Week 192 and Week 240.
- The proportion of subjects with ALT normalization at Week 48, Week 96, Week 144, Week 192 and Week 240 in subjects who have abnormal ALT at baseline, based on the lab report.
- The proportion of subjects with ALT normalization at Week 48, Week 96, Week 144, Week 192 and Week 240 in subjects who have abnormal ALT at baseline, based on AASLD criteria. Abnormal ALT by AASLD criteria is $\geq 19 \text{ U/L}$ for women and $\geq 30 \text{ U/L}$ for men.
- For HBeAg positive subjects: the proportion of subjects achieving HBeAg loss, HBeAg

seroconversion or HBsAg loss and HBsAg seroconversion at Week 48, Week 96, Week 144, Week 192 and Week 240.

- For HBeAg negative subjects: the proportion of subjects achieving HBsAg loss and HBsAg seroconversion at Week 48, Week 96, Week 144, Week 192 and Week 240.
- Incidence of virological breakthrough as defined by 1 log₁₀ IU/mL increase in HBV DNA from nadir (as determined by two sequential HBV DNA measurements at least 1 month apart, or the last on-treatment measurement) overall and by visit.
- The proportion of subject with unsatisfactory response overall and by each visit. Unsatisfactory response is defined as subjects who have HBV DNA ≥ 200 IU/mL at week 48 and afterwards have ≤ 1 log₁₀ IU/mL decrease in HBV DNA at two consecutive tests, confirmed by a third visit (additional visit) at least one month apart.
- The proportion of subjects with histological improvement (a reduction of two or more points in the Knodell necroinflammatory score with no increase in fibrosis) at Week 216 in the subset of subjects with paired baseline and Week 216 liver biopsies.
- The proportion of subjects with cirrhosis reversal (a reduction of one or more points in the Ishak score and no evidence of cirrhosis) at Week 216 in the subset of subjects with paired baseline and Week 216 liver biopsies and with a baseline Ishak score higher than or equal to five
- Change of fibrosis stage measured by LSM for subjects with baseline ALT > ULN and ALT \leq ULN, by baseline fibrosis stage. The fibrosis stage is measured by LSM value, based on the following rules:
 - For patient with baseline ALT > ULN: F0/1: LSM < 9.4 kPa, F2: 9.4 kPa \leq LSM < 12.4 kPa, F3: 12.4 kPa \leq LSM < 17.5 kPa, F4: LSM \geq 17.5 kPa
 - For patient with baseline ALT \leq ULN: F0/1: LSM < 6.0 kPa, F2: 6.0 kPa \leq LSM < 9.0 kPa, F3: 9.0 kPa \leq LSM < 12.0 kPa, F4: LSM \geq 12.0 kPa

Also, two-sided 95% CI will be calculated for each percentage.

Below endpoints will be summarized by descriptive statistics as the mean, standard deviation, minimum, median, maximum, and the number of observations.

- The mean changes of liver stiffness measurement (LSM) at Week 12, Week 24, Week 36, Week 48, Week 96, Week 144, Week 192 and Week 240 for patients with baseline ALT > ULN, baseline ALT ≤ ULN and overall.
- The mean log₁₀ IU/mL reduction in serum HBV DNA at Week 12, Week 24, Week 36, Week 48, Week 96, Week 144, Week 192 and Week 240 compared with baseline. And the result of log₁₀ HBV DNA at each visit will be summarized for whole period.

In addition, line plots of the proportion of subjects with HBV DNA < 20IU/mL and <69 IU/mL by visit, mean HBV DNA (log₁₀) over time by baseline ALT significance and a bubble plot for distribution of HBV DNA levels overtime will be provide. Newly diagnosed HCC, disease progression events, hepatitis B five item, liver stiffness measurement (LSM) and Childs-Pugh score will be listed.

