### Secondary Endpoints

- Incidence of HCC at Week 48, Week 96, Week 144, and Week 192
- Cumulative incidence of HCC at Week 48, Week 96, Week 144, Week 192 and Week 240
- Cumulative incidence of disease progression at Week 48, Week 96, Week 144 and Week 192, and Week 240
- The mean changes of liver stiffness measurement (LSM) at Week 48, Week 96, Week 144, Week 192 and Week 240
- Proportion of subjects with serum HBV DNA  $< 20$  IU/mL (Roche COBAS Taqman HBV Test) at Week 48, Week 96, Week 144, Week 192 and Week 240.
- The mean  $\log_{10}$  reduction in serum HBV DNA at Week 48, Week 96, Week 144, Week 192 and Week 240 compared with baseline.
- The proportion of subjects with ALT normalization at Week 48, Week 96, Week 144, Week 192 and Week 240 in subjects who have abnormal ALT at baseline.

- For HBeAg positive subjects: the proportion of subjects achieving HBeAg loss, HBeAg seroconversion or HBsAg loss and HBsAg seroconversion at Week 24, Week 48, Week 96, Week 144, Week 192 and Week 240.
- For HBeAg negative subjects: the proportion of subjects achieving HBsAg loss and HBsAg seroconversion at Week 48, Week 96, Week 144, Week 192 and Week 240.
- Incidence of virological breakthrough as defined by  $\geq 1 \log_{10}$  increase in HBV DNA from nadir (as determined by two sequential HBV DNA measurements at least 1 month apart, or the last on-treatment measurement) up to Week 48, Week 96, Week 144, Week 192 and Week 240
- The proportion of subjects with histological improvement (a reduction of two or more points in the Knodell necroinflammatory score with no increase in fibrosis) at Week 216 in the subset of subjects with paired baseline and W216 liver biopsies.
- The proportion of subjects with cirrhosis reversal (a reduction of one or more points in the Ishak score and no evidence of cirrhosis) at Week 216 in the subset of subjects with paired baseline and W216 liver biopsies and with a baseline Ishak score higher than or equal to five.
- Subject safety as determined by adverse events and laboratory assessments.

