Confirmation of HBV DNA test will require an additional visit to collect serum sample. To receive rescue treatment subjects must have investigational product (IP) compliance  $>$  80% in the last regular visits period (usually 12 weeks). Add-on combination with a nucleoside agent (LAM, ETV or LdT) is acceptable rescue treatment in this study, as to investigator's decision. Before rescue treatment, serum sample should be collected for resistance testing.

Subjects who reach primary endpoint (i.e. develop liver complications or HCC) may withdraw from study. Investigator and subjects can decide whether to continue study drug. Subjects who continue to take study drug will be followed as per the original schedule until Week 240. During the follow-up period, AEs, concomitant medication, vital signs, hepatitis B virus DNA, haematology, chemistry and prothrombin will be evaluated. Serum/plasma storage also will be conducted.

Supplementary study conduct information not mandated to be present in this protocol is provided in the accompanying Study Procedures Manual (SPM). The SPM will provide the site personnel with administrative and detailed technical information that does not affect subject safety.

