#### **4.4. Withdrawal Criteria**

Should a subject fail to attend the clinic for a required study visit, the site should attempt to contact the subject and re-schedule the missed visit as soon as possible. The site should also counsel the subject on the importance of maintaining the assigned visit schedule and ascertain whether or not the subject wishes to and/or should continue in the study based on previous non-compliance. In cases where the subject does not return for the rescheduled visit or cannot be reached to reschedule the missed visit, the site should make every effort to regain contact with the subject (3 telephone calls and if necessary a certified letter to the subject's last known mailing address) so that they can appropriately be withdrawn from the study. These contact attempts should be documented in the subject's medical record. Should the subject continue to be unreachable, then and only

then will he/she be considered to have withdrawn from the study with a primary reason of “Lost to Follow-up”. For all other subjects withdrawing from the study, an alternative reason for discontinuation should be recorded in the eCRF.

Subjects who temporarily interrupted treatment for <28 consecutive days were allowed to continue in the study. Subjects with treatment interruptions of  $\geq 28$  consecutive days were required to withdraw from the study.

A subject may voluntarily discontinue participation in this study at any time. The investigator also have the right to withdraw patients from treatment or the study in the event of intercurrent illness, adverse events, protocol violations, administrative reasons or other reasons at any time. Any female subject who becomes pregnant while participating should withdraw from the study. The reason for withdrawal from the study must be recorded in the case report form (CRF).

Subjects will also be withdrawn from the study if they reached primary end-point. These subjects will be eligible for study drugs and originally scheduled follow-up.

Subjects who have received at least one dose of study drug and permanently discontinued the study drug should be followed up by the investigator as described in Table 1.

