- 3 In the event of early study drug discontinuation, the evaluation should be performed in 12 weeks after discontinuation of study treatment.
- 4 Medical history will include any acute and chronic medical conditions including prior surgery, information related to hepatitis B history, any current and prior HBV medications, and previous HBV-related procedures.
- 5 Update any new medical conditions and/or concomitant medications that have occurred since study screening.
- 6 Concomitant medications including traditional Chinese medicines and/or herbal remedies.
- 7 At screening, a complete physical examination will be performed. For all following indicated visits, a brief physical examination will be performed.
- 8 Including blood pressure, pulse, respiratory rate and temperature.
- 9 Urine pregnancy test will be performed at screening, baseline and every 3 months after dosing.
- 10 HBV DNA will be tested using Roche COBAS Taqman HBV test(LLD 20 IU/mL).
- 11 Each study visit: All study medication to be collected and reconciled.

- 12 Liver biopsy will be done in 100 subjects in sites at baseline and week 216. Liver biopsy can be done at screening (Visit 1) or at baseline (Visit 2), at the discretion of investigator. Liver biopsy slides within 6 months prior to baseline can be accepted as baseline evaluation.
- 13 Tests will be performed at central lab
- 14 Demographic data includes birth date, gender and race
- 15 B ultrasound examination include liver, pancreas, spleen, gall bladder and kidney
- 16 Urinalysis: urine glucose, ketones, specific gravity, blood, pH and protein
- 17 Serum will be collected as scheduled for potential resistance surveillance. Genotypic analysis will be performed under the condition defined in protocol (see section 6.2.8)
- 18 Genotyping will be performed at central lab at screen

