3.2 Sample size

3.2.1 Sample size Assumptions

Sample sizes are chosen based on feasibility and precision because no hypothesis is tested in this study.

To decide the number of subjects for analysis, some precision calculations have been performed for the primary endpoint HCC incidence. In the retrospective analysis of GS-US-174-0102 and GS-US-174-0103 trials, HCC incidence over 7 years was approximately 4.5% among patients (23% of whom were Asian, 25 of whom were genotype B or C) with cirrhosis at baseline. Accordingly, we hypothesize that the accumulative incidence of HCC at 240 weeks will be 5% in Chinese compensated cirrhotic patients treated with TDF. The precision is calculated by the following:

$$Precision = Z_{1-\alpha/2} \sqrt{\frac{p(1-p)}{N}}$$

where Z is the critical value of normal distribution corresponding to the probability of $1-\alpha/2$ (corresponding to $(1-\alpha)*100\%$ confidence interval), and p is the percentage of patients who were diagnosed HCC during 240 weeks. Precision is half of the width of 95% confidence interval for the

point estimate. A sample size of 158 patients will allow us to estimate the confidence interval of the incidence with a margin of error at 3.4 % (0.016-0.084). Assuming a 15% drop out rate, 186 patients are to be recruited.

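### Histological improvement and cirrhosis reversal are reported only for subjects re-biopsied at Week 216, so both rates are likely to overstate the result among all subjects biopsied at baseline, and no companion figure bounds the effect

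*SAP*

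**What the plan says.** **Denominator.** SAP 7.4.2.3 gives the share with histological improvement "at Week 216 in the subset of subjects with paired baseline and Week 216 liver biopsies". Cirrhosis reversal is limited to those with "paired baseline and Week 216 liver biopsies and with a baseline Ishak score higher than or equal to five". The protocol's list of secondary endpoints has the same restriction: "in the subset of subjects with paired baseline and W216 liver biopsies". SAP section 9 lists one table per endpoint, 4.10.1 and 4.11.1, both labelled mITT.

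**Who is biopsied.** A footnote to Protocol Table 1 says: "Liver biopsy will be done in 100 subjects in sites at baseline and week 216". The biopsy row of that table has no entry in the withdrawal column.

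**After a primary endpoint event.** Protocol 3.1 makes withdrawal optional and keeps those who continue the drug on the planned visit schedule to Week 240. It then lists the assessments: "During the follow-up period, AEs, concomitant medication, vital signs, hepatitis B virus DNA, haematology, chemistry and prothrombin will be evaluated". Stored samples are added in the next sentence; biopsy is not mentioned. Protocol 4.4 states: "Subjects will also be withdrawn from the study if they reached primary end-point". Its next sentence nevertheless leaves these subjects eligible for study drug and for scheduled follow-up.

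**Missing data.** SAP 6.2 imputes nothing by default and specifies nothing for biopsies. Protocol 8.2.1 applies last observation carried forward to all endpoints, while Protocol 8.3.5 says missing values are in general not imputed.

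**The concern.** Whether a subject has a Week 216 biopsy depends partly on how the subject has fared. Death removes a subject with certainty, leaving the study removes the scheduled biopsy, and HCC or liver progression may do so. If those lost improve less often than those re-biopsied, the paired rate is higher than the rate among everyone biopsied at baseline.

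The secondary objective concerns the efficacy of 240 weeks of TDF in the study population. The study has one arm, so no control group would show the effect of selection. The mITT label on the tables also invites a broader reading than the paired subset supports. By contrast, SAP 7.4.1 plans two sensitivity analyses for HCC status missing at Week 240 because of COVID-19, and none is planned for missing biopsies.

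**Working it through.** **The plan's own figure.** The sample size was set for HCC incidence. With p = 5% and half-width 3.4%, 0.05 × 0.95 × (1.96/0.034)² = 157.85, so 158. The SAP adds: "Assuming a 15% drop out rate, 186 patients are to be recruited". 158/0.85 = 185.9, so 186. Both figures reproduce. The documents state no expected rate, precision or loss rate for the biopsy endpoints, so what follows is an illustration.

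**Inputs**
- Drop-out of 15% by Week 240 (SAP 3.2.1). This is study-wide and is borrowed here as an assumption for loss of the second biopsy.
- Paired rate r = 74%, the cirrhosis-reversal figure cited from earlier trials in Protocol 1.2. It is not a planning value.
- m, the improvement rate in subjects without a second biopsy. It is unknown, so a range is shown.

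**Formula.** With L the share lacking a Week 216 biopsy, the rate over all baseline biopsies is r(1 − L) + mL. The paired rate differs from this by L(r − m).

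**Loss by Week 216** at constant hazard: L = 1 − 0.85^(216/240) = 13.6%.

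**Gap at L = 13.6%, r = 74%**

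| Missing subjects | m | Rate over all baseline biopsies | Paired minus all |
|---|---|---|---|
| None improve | 0% | 63.9% | 10.1 points |
| Improve half as often | 37% | 69.0% | 5.0 points |
| Improve equally often | 74% | 74.0% | 0 |
| All improve | 100% | 77.5% | −3.5 points |

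**Other loss rates**, with no missing subject improving: the gap is 0.74 × L, which is 3.7 points at L = 5%, 7.4 at 10%, 11.1 at 15% and 18.5 at 25%.

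**A narrower case.** The only planning event rate is 5% HCC by Week 240. At constant hazard this is 1 − 0.95^(216/240) = 4.5% by Week 216. If only those subjects are lost as failures, and other missing subjects resemble the paired ones, the gap is 0.045 × 74 = 3.3 points. Other liver progression and death would add to it, but the documents give no rate for them.

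**The case against.** The paired population is openly declared, in the same terms in both documents. The endpoints are secondary and descriptive, with no hypothesis tested. The rate is valid for paired subjects. All this stands, and the point concerns only the step from paired subjects to all those biopsied at baseline.

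Three stronger readings are tempting, and the documents do not support them:

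- **That upward bias is certain.** It is positive only if missing subjects improve less often than paired ones. That is plausible after liver death or liver progression. It is an assumption for refusal, administrative withdrawal or renal-only progression; the progression endpoint includes creatinine clearance of 50 mL/min or less, which says nothing about histology.
- **That every subject with HCC or progression leaves the denominator.** Protocol 3.1, and the sentence in 4.4 after the withdrawal rule, allow such subjects to remain on the planned schedule, which includes the Week 216 biopsy. The list of post-event assessments omits biopsy, so the text is ambiguous.
- **That the 10-point gap is about twice the standard error.** With 85 pairs the standard error at 74% is √(0.74 × 0.26/85) = 4.8 points. But reversal counts only baseline Ishak 5 or more, while entry by biopsy admits Ishak 4, so the denominator may be well below 85. If half qualified (an assumption, about 43), the standard error is 6.7 points and the ratio about 1.5.

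Some information is available elsewhere. Liver stiffness is measured in all subjects, discontinuation reasons are summarised, and HCC and progression events are listed. None of this is planned specifically for the biopsy subset. The mock tables are in a separate document, so they may already show the counts. Finally, no random selection of the biopsy subset is described, so even a rate over all baseline biopsies need not represent all enrolled subjects.

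**Conclusion.** The concern holds as a likely overstatement of unknown size. Both histology rates exclude subjects who die or leave before Week 216, and possibly some with HCC or progression, and no specified analysis shows how much this matters. On the borrowed 15% drop-out and 74% reversal rate, the gap is at most about 10 points and about 5 points if missing subjects improve half as often. It vanishes if they improve equally often and reverses if they improve more often. Higher biopsy refusal would widen the possible range. The sample size and the primary endpoints are unaffected. This is a worthwhile, inexpensive addition to the reporting; it does not invalidate the planned analysis.

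**What to change.** 1. Keep the paired rates as planned.
2. In SAP 7.4.2.3 and Tables 4.10.1 and 4.11.1, add one supplementary rate per endpoint over all subjects with an evaluable baseline biopsy (for reversal, baseline Ishak 5 or more). Count a missing Week 216 biopsy as not improved and label the result a lower bound. A subject who has an event but is re-biopsied is scored on the biopsy.
3. In both tables show the number biopsied at baseline, the number paired, and the reasons for non-pairing: HCC, liver progression, renal-only progression, death, withdrawal, refusal.
4. Reconcile Protocol 3.1 and 4.4 on follow-up after a primary endpoint event, including whether the Week 216 biopsy applies. State in the SAP that the general carry-forward sentence in Protocol 8.2.1 does not govern the paired rates.

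Multiple imputation is not needed in so small a subset; the bound and the counts are enough.

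The cost is SAP wording and extra table rows. Baseline biopsies, event dates and disposition are already collected; the reason for a missed second biopsy should be confirmed as recorded. No visit or procedure is added. The downside is a second, less favourable and deliberately conservative figure beside the planned one.

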### 4.2. Inclusion Criteria

Specific information regarding warnings, precautions, contraindications, adverse events, and other pertinent information on the GSK investigational product or other study treatment that may impact subject eligibility is provided in the IB/IB supplement(s) and product label.

Deviations from inclusion criteria are not allowed because they can potentially jeopardise the scientific integrity of the study, regulatory acceptability or subject safety. Therefore, adherence to the criteria as specified in the protocol is essential.

Subjects eligible for enrolment in the study must meet all of the following criteria:

1. Age 18-60 years(inclusive);
2. Presence of HBsAg in serum at screening and for at least 6 months before screening assessment;
3. Serum HBV DNA  $\geq$  2000 IU/mL if HBeAg positive at screening (with or without ALT elevation); or serum HBV DNA  $\geq$  200IU/mL if HBeAg negative at screening (with or without ALT elevation);
4. Pathologically or clinically diagnosed as advanced fibrosis or compensated cirrhosis defined as one of following(a or b) :
  - a. Liver biopsy showing advanced fibrosis or cirrhosis (Ishak score  $\geq$ 4 or Fibrosis stage  $\geq$ S3 by Scheuer Score, or within the previous 6 months before baseline and provided that no treatment likely to improve liver histology has been taken since). The slides must be available for review by an independent histopathologist.
  - b. Clinical diagnosis: liver stiffness measure (LSM)  $>$ 12.4 kpa (ALT  $>$  ULN) or LSM  $>$ 9.0 kpa (ALT  $\leq$ ULN), (See section 6.2.7) plus one of the following:
    - i. Endoscopy-proven gastroesophageal or gastric varices, non-cirrhotic portal hypertension excluded;
    - ii. Abdominal ultrasound or CT found changes indicating cirrhosis, irregular liver surface or nodularity, with/without splenomegaly(depth of spleen  $>$ 4.0cm or spleen length  $>$ 13cm);
    - iii. Blood platelets  $<$ 100  $\times 10^9/L$  (and other causes of thrombocytopenia excluded);

5. Ability to give written informed consent;
6. A female is eligible to enter and participate in this study if she is of:
  - a. non-childbearing potential (i.e., physiologically incapable of becoming pregnant, including any female who is post-menopausal), or

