The relationship between baseline variables or on-treatment variables and improvement of fibrosis will be analysis by univariate and multivariate logistic model. Univariate analysis will include gender, age, BMI category (< 25 or ≥ 25 kg/m²), baseline HBV DNA (≥ 2000 or < 2000 , IU/mL), baseline HBeAg sero-status, baseline ALT value, baseline LSM value, baseline total bilirubin, HBeAg loss at Week 24, treatment response at Week 24 and Week 48, ALT normalized or not at Week 24 and Week 48, change from baseline of LSM at Week 12 and Week 24, change from baseline of GGT at Week 24. Multivariate analysis will include sex, age and the factors with $P \leq 0.20$ in univariate analysis.

Proportion of LSM improvement will be summarized at Week48, Week96, Week144, Week192 and Week240 for patients with baseline LSM result in following groups: LSM improved (LSM decreased from baseline $\geq 30\%$), LSM stable (LSM decreased from baseline $< 30\%$ or no change from baseline), and LSM deteriorate (LSM increase from baseline).

Proportion of fibrosis stage improvement will be summarized at Week 48, Week 96, Week 144, Week 192 and Week 240 for patients of fibrosis stage measured by fibrosis improved from baseline, ≥ 2 stage fibrosis stage improved from baseline, ≥ 1 stage fibrosis stage, no change from baseline, fibrosis stage increase from baseline.

Analyses of correlation coefficients between LSM and ALT level will be analyzed by Pearson correlation coefficients and P-value during every 48 weeks by patients with ALT normal at baseline, patients with abnormal at baseline and overall.

Correlation coefficients between variables change at Week 12 and 24 and LSM change at Week 240 will be analyzed by correlation coefficients and P-value. The change from baseline of Gamma-Glutamyltransferase (GGT), Total Bilirubin (TBIL), Albumin (ALB), International Normalized Ratio (INR) and LSM will be included in the analysis of correlation coefficients at Week 12, platelets (PLT), GPR, APRI, FIB-4 and all the variables included at Week 12 will be included in the analysis of correlation coefficients at Week 24.

A 5-years predicted HCC risks by REACH-B model (see Section 8.5) and observed HCC risks (cumulative incidence of HCC) at Week 240 will be presented in table. Decline in LSM from baseline to Week 240 by visit will be analyzed by a line plot.

In addition, a listing of HBV DNA result will be provided for the following patients:

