Table	4.7.3	The Proportion of Subjects Achieving HBsAg Loss and HBsAg Seroconversion at Week 48, 96, 144, 192 and 240 for Subjects with Negative HBeAg at Baseline - mITT
Table	4.8.1	Change from Baseline for the log ₁₀ IU/mL in Serum HBV DNA by Visit - mITT
Table	4.9.1	Incidence of Subjects Who Experience Viral Breakthrough by Visit - mITT
Table	4.9.3	Incidence of Subjects With Unsatisfied Response by Visit - mITT
Table	4.10.1	The Proportion of Subjects with Histological Improvement - mITT
Table	4.11.1	The Proportion of Subjects with Cirrhosis Reversal - mITT

Table	4.12.1	The Mean Changes of Liver Stiffness Measurement by Visit - mITT
Table	4.12.3.1.1	Shift from Baseline in Fibrosis Stage for Patients with Baseline ALT > ULN - mITT
Table	4.12.3.2.1	Shift from Baseline in Fibrosis Stage for Patients with Baseline ALT ≤ ULN - mITT
Table	4.12.3.3	Shift from Baseline in Fibrosis Stage - mITT
Table	4.13.1	Incidence of TDF Resistance Substitutions - mITT
Table	4.14.1	The Relationship Between Baseline Variables or On-treatment Variables and Newly Diagnosed Hepatocellular Carcinoma (HCC) - mITT
Table	4.14.3	The Relationship Between Baseline Variables or On-treatment Variables and Disease Progression - mITT
Table	4.17.1	Cox Regression Analysis for Time to Newly Diagnosed Hepatocellular Carcinoma (HCC) - mITT
Table	4.17.3	Cox Regression Analysis for Time to Disease Progression - mITT
Table	4.18.1	Impact of HBV DNA and Virologic Response on Change of LSM - mITT
Table	4.18.3	The Mean Changes of Liver Stiffness Measurement by Visit for Patients with Advanced Fibrosis and Compensated Cirrhosis - mITT
Table	4.18.3.1	The % Changes of Liver Stiffness from baseline by Visit for Patients with Advanced Fibrosis and Compensated Cirrhosis - mITT
Table	4.19.7	Cox Regression Analysis for Time to Improvement of Fibrosis - mITT
Table	4.20.3	The Relationship Between Baseline Variables or On-treatment Variables and Improvement of Fibrosis - mITT
Table	4.21.1	Proportion of LSM Improvement - mITT
Table	4.21.3	Proportion of LSM Stage Improvement - mITT
Table	4.22.1	Analyses of correlation coefficients between LSM and ALT level - mITT
Table	4.23.1	Analyses of correlation coefficients between Variables Change at Week 12 and 24 and LSM Change at Week240 - mITT
Table	4.24.1	Predicted and Observed Risk of HCC at Week240 - mITT
Table	5.3.4	Mean values in Non-invasive fibrosis - SA
Table	5.1.1	Overall Summary of Adverse Events - SA

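### LSM fibrosis stage is read on cut-offs fixed by baseline ALT, so when LSM and ALT fall together the tables can show regression that ALT-matched cut-offs do not; report the stage both ways

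*SAP*

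**What the plan says.** SAP 7.4.2.3 lists change in LSM-measured fibrosis stage as a secondary variable, split by baseline ALT and by baseline stage. The upper set of cut-offs begins "For patient with baseline ALT > ULN: F0/1: LSM < 9.4 kPa" and continues to 12.4 and 17.5 kPa. The lower set, for baseline ALT at or below ULN, begins "F0/1: LSM < 6.0 kPa, F2: 6.0 kPa" and continues to 9.0 and 12.0 kPa. SAP 6.1 defines baseline as the last assessment before study drug. No separate rule says which set to use after baseline.

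The stage then feeds several outputs:
- Table 4.12.3.1.1, "Shift from Baseline in Fibrosis Stage for Patients with Baseline ALT > ULN - mITT", its counterpart for normal baseline ALT (4.12.3.2.1), and a pooled shift table (4.12.3.3).
- SAP 7.4.3, "Proportion of fibrosis stage improvement will be summarized at Week 48, Week 96, Week 144, Week 192 and Week 240", which includes improvement by two or more stages, and Table 4.21.3.
- Figure 6.4.1, change of stage by visit.

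ALT normalisation among subjects with abnormal baseline ALT is itself a planned secondary endpoint at Weeks 48 to 240. No sensitivity analysis is specified for the stage outputs.

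**The concern.** Two sets of cut-offs make sense only if a given stiffness implies a different stage when ALT is raised. On that logic, the reason for the higher set lapses once ALT normalises, yet the subject stays on it for the rest of the study. A fall in LSM that accompanies ALT normalisation is then reported only as a fall in fibrosis stage. The study is single-arm, so no concurrent untreated group would show the same pattern and prompt caution. What is at stake is how the shift tables, the improvement proportions and the stage figure are interpreted. Neither primary endpoint uses LSM stage.

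**Working it through.** The SAP states no figure on misstaging, so there is none to reproduce. The check compares its two sets of cut-offs directly.

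**Inputs (SAP 7.4.2.3).** Raised-ALT set: 9.4 / 12.4 / 17.5 kPa. Normal-ALT set: 6.0 / 9.0 / 12.0 kPa. In both, the stage is F0/1 below the first cut-off, then F2, F3 and F4, with each cut-off belonging to the higher stage.

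**Step 1. Stage the same LSM on both sets.** For a subject with baseline ALT above ULN and current ALT at or below ULN:

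| LSM (kPa) | Fixed rule | Normal-ALT set | Levels lower |
|---|---|---|---|
| below 6.0 | F0/1 | F0/1 | 0 |
| 6.0 to <9.0 | F0/1 | F2 | 1 |
| 9.0 to <9.4 | F0/1 | F3 | 2 |
| 9.4 to <12.0 | F2 | F3 | 1 |
| 12.0 to <12.4 | F2 | F4 | 2 |
| 12.4 to <17.5 | F3 | F4 | 1 |
| 17.5 and above | F4 | F4 | 0 |

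The band that differs is 17.5 − 6.0 = 11.5 kPa wide. The two-level parts total 0.4 + 0.4 = 0.8 kPa (0.8 / 11.5 = 7%). The other 10.7 kPa differ by one level.

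**Step 2. Follow subjects whose ALT-matched stage does not change.** ALT is above ULN at baseline and normal later.
- F3 at both times: 12.4 to <17.5 kPa, then 9.0 to <12.0 kPa. On the fixed rule the later value is F0/1 (9.0 to <9.4) or F2 (9.4 to <12.0), so it is always reported as improved.
- F2 at both times: 9.4 to <12.4 kPa, then 6.0 to <9.0 kPa. The later value is always F0/1, so it too is always reported as improved.
- F4 at both times: 17.5 kPa or more, then 12.0 kPa or more. The later value is F3 or F2 unless LSM remains at 17.5 kPa or above.

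**Step 3. LSM fall that leaves the ALT-matched stage boundary unchanged.** Fall = 1 − normal-ALT cut-off / raised-ALT cut-off.
- F0/1–F2: 1 − 6.0/9.4 = 36%.
- F2–F3: 1 − 9.0/12.4 = 27%.
- F3–F4: 1 − 12.0/17.5 = 31%.

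**Step 4. Opposite directions.**
- LSM unchanged while ALT normalises: the fixed rule gives no stage change.
- Baseline ALT normal, later raised: the subject stays on the lower set and is staged too high relative to the raised-ALT set, over the same 6.0 to <17.5 kPa band.
- Visit-ALT rule, LSM 15.0 to 13.0 kPa (2.0/15.0 = 13% fall) with ALT normalising: F3 to F4, an apparent worsening.
- Visit-ALT rule, 17.4 to 12.1 kPa (5.3/17.4 = 30.5% fall) with ALT normalising: F3 to F4, although SAP 7.4.3 would class the same subject as LSM improved (fall of at least 30%).

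**Step 5. The pooled table.** Two subjects at 11 kPa with normal ALT at Week 240 are F2 and F3 in Table 4.12.3.3 if one had raised and the other normal ALT at baseline.

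**The case against.** Holding one set of cut-offs constant is a defensible choice for a change-from-baseline measure. It prevents a stage change when LSM has not moved, whereas switching sets creates false worsening (Step 4). That stands, and it rules out visit-ALT staging as the sole rule.

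Several stronger readings are tempting but not supported:
- A reader might infer that ALT normalisation by itself appears as regression. It does not; LSM must fall across a cut-off.
- A reader might infer that the fixed stage is wrong and the visit-ALT stage right. The documents validate neither set for restaging on treatment. Lower here means lower than the SAP's other set.
- A reader might cite entry criterion 4b ("Clinical diagnosis: liver stiffness measure (LSM" above 12.4 or 9.0 kPa according to ALT) as proof that the plan elsewhere uses ALT at the visit. The criterion does not say when ALT is taken, and at entry visit ALT and baseline ALT are practically the same.
- A reader might estimate the share affected by multiplying assumed rates of raised baseline ALT and of normalisation. The documents give neither rate, and the product would also count subjects below 6.0 or at or above 17.5 kPa, who are staged identically.

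The plan also offers context: shift tables split by baseline ALT, mean LSM change in the same groups, LSM–ALT correlations, and paired biopsies read blind to timing in about 100 subjects. The stratum with normal baseline ALT cannot show false regression from ALT normalisation. These help an attentive reader, but they restage no one and leave the pooled table, Table 4.21.3 and Figure 6.4.1 as they are.

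**Conclusion.** The point holds as a gap in reporting. For subjects with baseline ALT above ULN whose ALT normalises, the fixed rule gives a stage one level below the SAP's own normal-ALT set throughout 6.0 to <17.5 kPa, and two levels below in two 0.4 kPa slivers. Where LSM and ALT fall together, the stage outputs can show regression that ALT-matched cut-offs do not. The reverse error applies to subjects with normal baseline ALT whose ALT later rises.

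This rests on two readings: that the baseline-ALT set applies at every visit, since no other rule is given, and that the stage in SAP 7.4.3 and Figure 6.4.1 is the one defined in 7.4.2.3. The number of subjects affected cannot be computed, because the documents contain no LSM or ALT distribution. The consequence is limited to descriptive secondary and exploratory outputs in a study that tests no hypothesis.

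**What to change.** In SAP 7.4.2.3 and 7.4.3, report the stage shift and the stage-improvement proportions twice: with the set fixed by baseline ALT, and with the set matched to ALT at each visit. State that a result will be described as stage regression only if it holds under both. Give Figure 6.4.1 the same two versions. Optionally, add a shift from the first on-treatment visit with normal ALT, using the normal-ALT set throughout.

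No new data are needed, since Protocol Table 1 schedules FibroScan and chemistry at every visit. The cost is some SAP wording, one extra derivation and one extra set of tables. The visit-ALT version can show false worsening when ALT normalises with little change in LSM, so it should sit beside the fixed version and not replace it.
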